6.3 Duration of Therapy

In the absence of treatment delays due to adverse event(s), treatment may continue for 7 days or until one of the following criteria applies:

- Intercurrent illness that prevents further administration of treatment
- Unacceptable adverse event(s)
- Patient decides to withdraw from the study
- General or specific changes in the patient's condition render the patient unacceptable for further treatment in the judgment of the investigator
- Patient non-compliance
- Termination of the study by sponsor
- The drug manufacturer can no longer provide the study agent

The reason(s) for protocol therapy discontinuation, the reason(s) for study removal, and the corresponding dates must be documented in the Case Report Form (CRF).

6.4 Duration of Follow-Up

Patients will be followed for 60 days after beginning the 7. day course of neoral or until death, whichever occurs first. Please refer to the schedule of events (**Table 1**), below. Patients experiencing adverse event(s) that require cessation of Neoral will be followed until resolution or stabilization of the adverse event.

6.5 Missing Data

To minimize missing data, we will differentiate treatment discontinuation from study withdrawal. Study withdrawal will be considered as withdrawal of consent or loss of follow-up.

7. DOSING DELAYS/DOSE MODIFICATIONS

- 7.1.1 The dose of Neoral is 2.5mg/kg PO BID, based on the renal transplant dose, and Neoral will be administered for 7 days.
- 7.1.2 A blood cyclosporine trough level will be obtained on day 3 to avoid toxicity due to high concentrations. If this level is greater than 250 ng/ml, the Neoral dose will be decreased by 25-50%. If the level is 250 ng/ml or less, no modifications will be made.
- 7.1.3 Cyclosporine trough levels will be also obtained on day 6 and day 9. If this level is greater than 250 ng/ml on day 6 the Neoral dose will be decreased by 25-50% for the rest of the study period (7 days).

8. STUDY CALENDAR

Table 1 Schedule of Study Events (Part 1)

Visit	Screening	Baseline	Treatment ¹							Follow-up ²		
	1	2	3	4	5	6	7	8	9	10		
Study Day	-21 to -1	-2 to 0	1	2	3	4	5	6	7	8	9	10
Written Informed Consent	X											
Assign Screening Number	X											
Complete Medical History	X											
Demographics	X											
Inclusion/Exclusion Criteria Review	X											
WHO COVID-19 Severity Scale	X	X	X	X	X	X	X	X	X	X	X	X
Assign Enrollment Number		X										
Complete Physical Examination	X	X	X	X	X	X	X	X	X	X	X	X
Vital Signs (BP, HR, RR, Temp, SpO ₂)	X	X	X	X	X	X	X	X	X	X	X	X
FIO ₂ Assessment	X	X	X	X	X	X	X	X	X	X	X	X
Pregnancy Test for Female Patients	X											
Cyclosporine Administration			X	X	X	X	X	X	X			
12-Lead ECG	X								X			X
Chest X-ray	X								X			X
BMP	X	X	X	X	X	X	X	X	X	X	X	X
LFTs	X	X	X	X	X	X	X	X	X	X	X	X
CBC	X	X	X	X	X	X	X	X	X	X	X	X
ANC	X	X	X	X	X	X	X	X	X	X	X	X
Absolute Lymphocyte Count	X	X	X	X	X	X	X	X	X	X	X	X
Total Cholesterol	X	X										
Ferritin	X	X	X	X	X	X	X	X	X	X	X	X
D-Dimer	X	X	X	X	X	X	X	X	X	X	X	X
CRP	X	X	X	X	X	X	X	X	X	X	X	X
LDH	X	X	X	X	X	X	X	X	X	X	X	X
Magnesium	X	X	X	X	X	X	X	X	X	X	X	X
Phosphorus	X	X	X	X	X	X	X	X	X	X	X	X
PT/PTT	X	X							X			
SARS-CoV-2 PCR	X											
AE Assessment	Continuous Monitoring from Signing of the Informed Consent-----►											
Concomitant Medications/Therapies	Continuous Monitoring from Signing of the Informed Consent-----►											

ANC =Absolute neutrophil count; BMP =basic metabolic panel; BP = blood pressure; CBC = complete blood count; CRP =c-reactive protein; ECG = Electrocardiogram; FIO₂ = oxygen requirement; HR = heart rate; LDH = lactate dehydrogenase; LFTs = liver function tests; PT = prothrombin time; PTT = partial thromboplastin time; RR = respiratory rate; SpO₂ = oxygen saturation; WHO = World Health Organization.

¹Treatment assessments will be performed every 24±6 hours. Treatment is Neoral for 7 days and will discontinued on the day of discharge if the patient is discharged before the 7d course is completed. If the patient is discharged before 7 days, the patient will not undergo any assessments until the first outpatient visit.

²Follow up will be performed every 24±6 hours while inpatient. Once patient is discharged, follow up will be at days 14±3 days, 28±3 days, and 60±3 days either by in person clinic visit or telemedicine visit.

Table 1 Schedule of Study Events (Part 2)

Visit	Follow-up ²							
	11	12	13	14	15-27	28	60	
Study Day	11	12	13	14	15-27	28	60	
Written Informed Consent								
Assign Screening Number								
Complete Medical History								
Demographics								
Inclusion/Exclusion Criteria Review								
WHO COVID-19 Severity Scale	X	X	X	X	X	X	X	
Assign Enrollment Number								
Complete Physical Examination	X	X	X	X	X	X		
Vital Signs (BP, HR, RR, Temp, SpO ₂)	X	X	X	X	X	X		
FIO ₂ Assessment	X	X	X	X	X	X		
Pregnancy Test for Female Patients								
Cyclosporine Administration								
12-Lead ECG								
Chest X-ray								
BMP	X	X	X	X	X	X		
LFTs	X	X	X	X	X	X		
CBC	X	X	X	X	X	X		
ANC	X	X	X	X	X	X		
Absolute Lymphocyte Count	X	X	X	X	X	X		
Ferritin	X	X	X	X	X	X		
D-Dimer	X	X	X	X	X	X		
CRP	X	X	X	X	X	X		
LDH	X	X	X	X	X	X		
Magnesium	X	X	X	X	X	X		
Phosphorus	X	X	X	X	X	X		
PT/PTT	X	X	X	X	X	X		
Cyclosporine Level ³								
SARS-CoV-2 PCR				X		X	X	
AE Assessment	-----Continuous Monitoring from Signing of the Informed Consent-----►							
Concomitant Medications/Therapies	-----Continuous Monitoring from Signing of the Informed Consent-----►							

ANC =Absolute neutrophil count; BMP =basic metabolic panel; BP = blood pressure; CBC = complete blood count; CRP = c-reactive protein; ECG = Electrocardiogram; FIO₂ = oxygen requirement; HR = heart rate; LDH = lactate dehydrogenase; LFTs = liver function tests; PT = prothrombin time; PTT = partial thromboplastin time; RR = respiratory rate; SpO₂ = oxygen saturation; WHO = World Health Organization.

¹Treatment assessments will be performed every 24±6 hours. Treatment is Neoral for 7 days and will begin as an inpatient and will be discontinued if the patient is discharged before the 7d course is completed. If the patient is discharged before 7 days, the patient will not undergo any assessments until the first outpatient visit.

²Follow up will be performed every 24±6 hours while inpatient. Once patient is discharged, follow up will be at days 14±3 days, 28±3 days, and 60±3 days either by in person clinic visit or telemedicine visit.

³Cyclosporine trough levels will be checked on day 3. If >250 mg/ml, the dose will be decreased by 25-50%. Additional levels will be at the discretion of treating physicians but will be performed on day 6 and day 9 if the participant is an inpatient.

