6. TREATMENT AND/OR IMAGING PLAN

6.1 Agent Administration

Treatment will be administered on an inpatient basis. Reported adverse events and potential risks are described in Section 10. Appropriate dose modifications are described in Section 7

Arm A Regimen Description					
Agent	Premedications; Precautions	Dose	Route	Schedule	Cycle Length
Neoral, Investigational, Generic Acceptable,	NA	2.5 mg/kg	PO	BID	7 days

N=50 Patients					

Arm B Regimen Description					
Agent	Premedications; Precautions	Dose	Route	Schedule	Cycle Length
None*, N= 25 Patients	NA	NA	NA	NA	7 days

*Note: The PI has undertaken thorough discussions with the sponsor and generation of placebo capsules is not feasible for the timing of this study.

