11.1 Primary Endpoint and Analytic Plan

The primary endpoint is the clinical outcome based on the World Health Organization (WHO) COVID Ordinal Clinical Improvement Scale (Table 2) on day 14. Wilcoxon rank sum test will be used to compare the ordinal scale between groups on day 14.

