11.4.2 Intent to treat (ITT) population

All randomized patients in the study will be assessed for response to treatment, even if there are major protocol treatment deviations. Each patient will be assigned one of the WHO COVID scale categories outlined in **Table 2**. Primary and secondary objectives will be analyzed.

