11.4.3 Modified intent to treat (MITT) population

Primary and secondary objectives will be analyzed in all randomized patients who complete 7 days of Neoral.

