11.4.4 Per-protocol analysis population

Sub-analyses may then be performed on the basis of a subset of ITT population, excluding those for whom major protocol deviations have been identified (e.g., early death due to other reasons, early discontinuation of treatment, major protocol violations, etc.). However, these sub-analyses

may not serve as the basis for drawing conclusions concerning treatment efficacy, and the reasons for excluding patients from the analysis should be clearly reported.

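### Section 11.4.3 defines an analysis set for the primary objective by completion of 7 days of Neoral: as written it has no controls, otherwise it is selected on outcome, and no section ranks it below ITT

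*Combined protocol and SAP*

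**What the plan says.** **Analysis sets.** Section 11.4.2 (ITT) takes all randomized patients, "even if there are major protocol treatment deviations", and covers the primary and secondary objectives. Section 11.4.3 (MITT) covers the same objectives in a different set: "Primary and secondary objectives will be analyzed in all randomized patients who complete 7 days of Neoral". Section 11.4.4 (per-protocol) allows sub-analyses in a subset of ITT, gives early discontinuation of treatment as an example of a major deviation, and says these sub-analyses "may not serve as the basis for drawing conclusions concerning treatment efficacy". That caution is not repeated in 11.4.3.

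**Primary test.** Section 11.1 says "Wilcoxon rank sum test will be used to compare the ordinal scale between groups on day 14". It does not say in which set.

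**Treatment.** In section 6.1 the Arm B agent is given as "None*, N= 25 Patients". The same section says "Treatment will be administered on an inpatient basis". The explicit stopping rule is in section 8: Neoral "will discontinued on the day of discharge if the patient is discharged before the 7d course is completed" (Table 1 Part 1, footnote 1), repeated in Part 2 as "will be discontinued if the patient is discharged before the 7d course is completed". Sections 1.1.1, 7.1.1 and 11.4.1 speak of 7 days without this exception, and the list of stopping reasons in 6.3 omits discharge.

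**The concern.** A patient who recovers and goes home on day 5 has followed the protocol exactly, yet has not completed 7 days of Neoral and falls outside the 11.4.3 set. So does a patient who dies on day 4 or stops for toxicity. Both events bear directly on the day-14 WHO score. Losing early discharges from the Neoral arm alone makes Neoral look worse. Losing early deaths makes it look better, as do toxicity stops if those patients fare worse. Controls take no Neoral, so the text either removes all of them or leaves the reader to guess how they are filtered.

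At stake is a second analysis of the primary objective that is either impossible or no longer a randomized comparison. It sits in an open-label trial of 75 patients whose plan does not state in writing which set decides the result.

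**Working it through.** **1. Literal reading.** Membership requires 7 completed days of Neoral, and Arm B receives none. The set therefore contains 0 of the 25 controls and supports no comparison. This needs no assumed rate.

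**2. The plan's own figure.** Inputs from Table 3 (section 11.2), categories 1 to 8:
- Control: 23, 24, 10, 5, 5, 8, 8, 17%.
- CSA Scenario 1: 39, 39, 2, 2, 2, 4, 4, 8%.

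P1 = Pr(Control > CSA) + ½ Pr(tie) = 0.5466 + 0.1037 = 0.650, as stated.

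Noether power for 25 and 50 at one-sided 10% is Φ(√(12 × 1/3 × 2/3 × 75) × 0.150 − 1.282) = Φ(2.125 − 1.282) = 80.0%. Simulation with a tie-corrected Wilcoxon test gives 82.7%. The stated 81% is sound.

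**3. Assumed early losses.** The documents give no rate of discharge or death before day 7. As an assumption, take constant hazards that reach Table 3's day-14 shares, and count events by day 6:
- Discharged (categories 1 and 2), no effect: 1 − (1 − 0.47)^(6/14) = 23.8%, or 12 of 50.
- Discharged, Scenario 1: 1 − (1 − 0.78)^(6/14) = 47.7%, or 24 of 50.
- Dead (category 8), no effect: 1 − (1 − 0.17)^(6/14) = 7.7%, or about 4 of 50.
- Dead, Scenario 1: 1 − (1 − 0.08)^(6/14) = 3.5%, or about 2 of 50.

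Patients enter on oxygen, so a constant discharge hazard from day 0 is probably too high. Half the discharges is therefore shown as well.

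**4. Filter applied to Neoral only, all 25 controls kept.** Remove these shares from categories 1 and 2 (in proportion) and from category 8, renormalise, and recompute. Example, no effect with discharges and deaths: 1 − 0.238 − 0.077 = 0.685 of the arm remains (34 of 50), and P1 = 0.454.

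| Dropped from Neoral | No effect: P1 | Rejects at 10% | Scenario 1: P1 | Power |
|---|---|---|---|---|
| Nobody | 0.500 | 10% | 0.650 | 83% |
| Discharges only | 0.417 | 1% | 0.543 | 23% |
| Discharges and deaths | 0.454 | 3% | 0.576 | 37% |
| Half the discharges, and deaths | 0.500 | 10% to 11% | 0.639 | 74% to 75% |
| Deaths only | 0.534 | 22% | 0.671 | 89% |

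With these deaths dropped and no drug effect, the bias cancels when 12% (6 of 50) are discharged early. Fewer early discharges favour Neoral; more disfavour it.

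**5. Same 7-day filter applied to both arms.** With no effect, P1 is 0.500 and rejection about 10% in every case. Scenario 1 power is 54% to 55% with full discharges and deaths, and 73% with half the discharges and deaths.

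**6. Not counted.** Toxicity stops, and intubated patients who cannot finish oral dosing.

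**The case against.** **ITT is plainly the intended primary set.** It covers all randomized patients, and the powered 25 and 50 are the planned arm sizes in 6.1. A completer set resembles the per-protocol subset that 11.4.4 already limits. This is a fair reading of intent, and nothing shows that the sponsor would treat MITT as co-primary; a reader might infer that, but the text does not say it. What remains is that 11.1 names no set and that the caution in 11.4.4 refers to its own sub-analyses only.

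**The 7-day rule could apply to both arms.** Section 6.1 gives Arm B a 7-day cycle length. On that reading the no-effect bias disappears (step 5). The wording of 11.4.3 does not say this, however, and the loss of power and the selection on outcome remain.

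**The sizes rest on assumptions.** They do. In the half-discharge case the no-effect result is essentially unbiased. The 22% in the deaths-only row depends on 7.7% of Neoral patients dying by day 6; with 1%, 2% or 4% it is about 11%, 12% to 13% and 15%. That row matters only if 11.4.3 were patched to count discharge as completion.

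**The durations do not conflict.** A reader might infer that the 7-day statements contradict the stop at discharge. They can be reconciled: footnote 1 itself gives 7 days and then the exception, 6.3 permits treatment for 7 days rather than requiring it, and no section tells sites to dose after discharge. Section 6.1 says only that treatment is inpatient.

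**Conclusion.** Section 11.4.3 is wrong as written. Literally it has no control arm; with controls retained it conditions on events after randomization that are part of the outcome. The first conclusion rests on the text alone.

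The size and direction of the bias are unknown. Under the assumed hazards, dropping discharges and deaths from Neoral only gives a no-effect P1 of 0.45 to 0.50, a false-positive rate of 3% to 11% and Scenario 1 power of 37% to 75%. Filtering both arms gives a no-effect P1 of 0.50 and power of 54% to 73%.

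Two stronger conclusions might be inferred and are not supported. One is that the trial's main comparison is compromised: the ITT analysis, the sample size and the 81% power stand. The other is that the completer set reliably favours or disfavours Neoral: that depends on a mix of early discharges, deaths and toxicity stops that the documents do not give. The plan should be changed on this point.

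**What to change.** (a) In 11.1, name the ITT population of 11.4.2 as the primary analysis set.

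(b) Delete 11.4.3. Alternatively, redefine it without reference to completing the course, include all controls, label it supportive and place it under the caution in 11.4.4. A rule of at least one dose received is better than completion but still filters Neoral only, and 4.2 allows 2 days before the first dose. If it is used, report never-dosed Neoral patients by reason and keep them in ITT, even where 4.2 would allow their registration to be cancelled. Counting discharge as completion is not enough, because early deaths would still be dropped.

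(c) In 11.4.4, state that stopping Neoral at discharge under Table 1, footnote 1 is neither a protocol deviation nor early discontinuation.

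The cost is a few lines of text and the loss of the completer analysis; sample size and power do not change. Two optional clarifications, not corrections of errors: add the discharge exception to 1.1.1, 6.3, 7.1.1 and 11.4.1, and tabulate doses received by reason for stopping. The data for that table are already required by 6.3 and 13.2.1.

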1.2 Secondary Objectives

- 1.2.1 To establish the safety of Neoral in this patient population (adverse events).
- 1.2.2 To determine the effect of Neoral on serum inflammatory markers (CRP, d-dimer, ferritin, ANC, absolute lymphocyte count, WBC, PLT (daily while inpatient and including day 14 and 28 for those discharged).
- 1.2.3 To determine the effect Neoral on viral SARS-CoV2 PCR positivity from baseline (day 0 to -2) before receiving Neoral) to day 14, and from baseline to day 28.
- 1.2.4 To determine the effect of Neoral on survival (days 14 and 28)
- 1.2.5 To determine the effect of Neoral on disease improvement (alive and free of invasive or non-invasive mechanical ventilation; days 14 and 28).
- 1.2.6 To determine the effect of Neoral on proportion of those requiring invasive mechanical ventilation.
- 1.2.7 To determine the effect of Neoral on incidence of deep vein thrombosis.
- 1.2.8 To determine the effect of Neoral on proportion of patients discharged on day 28.
- 1.2.9 To determine the effect of Neoral on time to hospital discharge.
- 1.2.10 To determine the effect of Neoral on disease resolution (alive and discharged home without oxygen; days 14 and 28).

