5.1 Specimen Collection

Blood biomarkers will be drawn as described in **Table 1** (Schedule of Events).

1. Blood biomarkers are all standard hospital tests with standard blood draw collection protocols.
2. SARS-CoV-2 viral positivity will be determined from nasopharyngeal swabs using in-house hospital real-time RT-PCR by the Cepheid GeneXpert platform. Both nostrils will be used for virologic assessment. Please see the package insert for full detail.

(<https://www.cepheid.com/Package%20Insert%20Files/Xpress-SARS-CoV-2/Xpert%20Xpress%20SARS-CoV-2%20Assay%20ENGLISH%20Package%20Insert%20302-3750%20Rev.%20C.pdf>)

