11.5 Analysis of Secondary Endpoints

The secondary objectives are mostly concerned with the safety and effects of Neoral (CSA) in this patient population. The secondary endpoints include Neoral-associated toxicity events, serum inflammatory markers (CRP, d-dimer, ferritin, ANC, absolute lymphocyte count, WBC, PLT (daily while inpatient and including day 14 and 28 for those discharged), Viral load (days 14 and 28), vital status (days 14 and 28), disease improvement (days 14 and 28), proportion of those requiring invasive mechanical ventilation, incidence of deep vein thrombosis, proportion of patients discharged on day 28, time to hospital discharge, and disease resolution (days 14 and 28).

For safety, Neoral-associated toxicity events include nephrotoxicity, resistant hypertension, hepatotoxicity, signs of CNS toxicity, or superinfection. AE's and SAE's by CTCAE v5 will be summarized descriptively with frequencies and rates. Rates and 95% CI's of grade 3 and above AE's will be reported.

Serum inflammatory markers are viewed as interval scales and after appropriate normalizing transformation (if needed), will be analyzed using general linear mixed models to account for within patient dependencies to allow comparisons between groups.

Viral positivity between groups at days 14 and days 28 will be tested by Wilcoxon rank sum test.

Survival analysis methods will be used to describe overall survival experience, to estimate survival at selected time points, and to compare groups. Cumulative incidence analysis methods will be used if there are competing risks. The same approach will be used with disease improvement (alive and free invasive or non-invasive mechanical ventilation) and disease resolution (alive and discharged home without oxygen).

Fisher's exact test will be used to compare rates of need for invasive mechanical ventilation bench marked to a particular time, and ever need. If required, this endpoint will include deaths before intubation in the rare cases in which this occurs.

In exploratory analyses, we will use logistic regression to model ventilator need as a function of treatment group and other baseline characteristics. Survival analysis methods will be used to analyze time to mechanical ventilation, with censoring at last follow-up for those not needing ventilation.

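### Days 14 and 28 need blood and swabs, but discharged patients may be seen by telemedicine, so samples could be missing according to discharge; separately, Table 1 does not guarantee a PCR in the baseline window.

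*Combined protocol and SAP*

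**What the plan says.** **Specimens required.** Objective 1.2.2 (section 1.2) wants the inflammatory markers "daily while inpatient and including day 14 and 28 for those discharged". Objective 1.2.3 wants "PCR positivity from baseline (day 0 to -2) before receiving Neoral) to day 14, and from baseline to day 28". Section 5.1 states that "SARS-CoV-2 viral positivity will be determined from nasopharyngeal swabs", run on the hospital's own platform, and section 5.2.1 sends all specimens to the site hospital laboratories. Table 1, Part 2 (section 8) marks the blood markers at days 14 and 28 and PCR at days 14, 28 and 60, with no exemption for discharged patients.

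**Visits allowed.** Footnote 2 to Table 1 has inpatients assessed every 24±6 hours. After discharge, the visits at days 14, 28 and 60 may be "either by in person clinic visit or telemedicine visit". Footnote 1 adds: "If the patient is discharged before 7 days, the patient will not undergo any assessments until the first outpatient visit".

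**Baseline PCR.** The Table 1, Part 1 header gives Screening and then Baseline as "Study Day -21 to -1 -2 to 0 1". The PCR row is "SARS-CoV-2 PCR X", a single mark in the first column, Screening. CRP, D-dimer and ferritin are marked in both columns. Criterion 3.1.1 accepts a confirmed infection from the past 10 days.

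**Analysis.** Section 11.5 fits general linear mixed models to the markers. For PCR it says: "Viral positivity between groups at days 14 and days 28 will be tested by Wilcoxon rank sum test". Section 6.5, on missing data, separates stopping treatment from leaving the study. It does not address a visit that takes place without specimens.

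**The concern.** A telemedicine contact yields neither blood nor a swab, and the protocol describes no home, local or laboratory-only collection. A site that uses telemedicine at day 14 or 28 complies with footnote 2 and still loses the specimens that the objectives need.

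The loss would not fall at random. Inpatients are sampled; discharged patients may not be. Section 11.2 expects Neoral to send less ill patients home sooner, so the patients sampled at day 14 would be selected by an event after randomisation that is expected to differ between arms. That could distort the comparison of PCR positivity and, to a lesser degree, of the markers.

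The baseline PCR is a separate defect. Objective 1.2.3 is framed as a change from a value taken on day 0 to -2, and the schedule does not ensure that such a value exists.

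**Working it through.** **1. The plan's own figure.** Table 3 supplies the day-14 distribution used below, so I first checked that it gives the stated power. For Scenario 1, P1 = P(Control > CSA) + ½·P(tie) = 0.5466 + ½ × 0.2073 = 0.650, against the stated 0.65. Noether's formula with N = 75, control fraction c = 1/3 and one-sided α = 10%:

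power = Φ(√(12·c·(1−c)·N) × (P1 − 0.5) − z₀.₉₀) = Φ(14.14 × 0.1503 − 1.2816) = 80%.

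Simulating the tie-corrected rank-sum test gives 82.8%. The stated 81% is reproduced to within 2 points.

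**2. Expected day-14 status.** Discharged = scores 1–2; in hospital = scores 3–7; dead = score 8. Percentages are from Table 3, applied to 25 control and 50 Neoral patients.

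| | In hospital (H) | Discharged (D) | Dead |
|---|---|---|---|
| Control | 36% = 9.0 | 47% = 11.75 | 17% = 4.25 |
| Neoral, Scenario 1 | 14% = 7.0 | 78% = 39.0 | 8% = 4.0 |
| Neoral, Scenario 2 | 20% = 10.0 | 70% = 35.0 | 10% = 5.0 |
| Neoral, Scenario 3 | 24% = 12.0 | 64% = 32.0 | 12% = 6.0 |

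**3. Share of survivors sampled.** Let t be the share of discharged patients seen by telemedicine. The documents do not give it. I assume that it is the same in both arms and run it from 0 to 100%. Sampled share = [H + (1−t)·D] / (H + D).

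| t | Control | Neoral Sc. 1 | Neoral Sc. 2 | Neoral Sc. 3 |
|---|---|---|---|---|
| 0 | 100% | 100% | 100% | 100% |
| 50% | 14.875/20.75 = 72% | 26.5/46 = 58% | 27.5/45 = 61% | 28/44 = 64% |
| 100% | 9/20.75 = 43% | 7/46 = 15% | 10/45 = 22% | 12/44 = 27% |

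With a common t above zero, the arms differ whenever Neoral speeds discharge.

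**4. When do inpatients supply most of the samples?** Both arms combined, this needs H > (1−t)·D, that is t > 1 − H/D:
- Scenario 1: 1 − 16/50.75 = 68%
- Scenario 2: 1 − 19/46.75 = 59%
- Scenario 3: 1 − 21/43.75 = 52%

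**5. Direction of bias in the PCR comparison.** For illustration only, assume 70% positivity in inpatients and 40% in discharged patients (neither figure is in the documents). Observed rate = [0.7·H + 0.4·(1−t)·D] / [H + (1−t)·D], Scenario 1:

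| t | Control | Neoral | Difference (points) |
|---|---|---|---|
| 0 | 11.0/20.75 = 53.0% | 20.5/46 = 44.6% | 8.4 |
| 50% | 8.65/14.875 = 58.2% | 12.7/26.5 = 47.9% | 10.2 |
| 75% | 7.475/11.9375 = 62.6% | 8.8/16.75 = 52.5% | 10.1 |
| 90% | 6.77/10.175 = 66.5% | 6.46/10.9 = 59.3% | 7.3 |
| 100% | 70% | 70% | 0 |

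The difference first widens, then narrows, and vanishes only at 100%.

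**6. Baseline PCR.** Required window: day 0 to -2. Scheduled window: day -21 to -1. They overlap on days -2 and -1 only. A screening swab on day -3 or earlier satisfies the schedule but not the objective.

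Day 28 cannot be sized, because the documents give no day-28 distribution.

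**The case against.** Table 1 does schedule the specimens at days 14 and 28, marks a physical examination on the same days, and allows in-person visits. If sites bring patients in, nothing is lost. This stands: the defect is that the footnote permits the loss, not that it is certain.

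Several stronger readings are tempting, and the documents do not support them:

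- *Day-14 samples will come mainly from patients still in hospital.* That needs more than about 52–68% of discharged patients on telemedicine, a share the documents do not give.
- *The marker comparison reduces to inpatients.* The mixed model also uses baseline and daily inpatient values, so discharged patients still contribute. The protection is partial: it relies on the observed values explaining what is missing after discharge, and under footnote 1 a patient discharged before day 7 has no values until the first outpatient visit.
- *A true PCR difference would disappear.* In the illustration it does so only at 100% telemedicine; at 50% it is slightly larger than with full sampling.
- *The baseline gap biases the planned PCR test, or helps to select sicker patients.* Section 11.5 compares the arms at days 14 and 28 without a baseline value, and the gap has no bearing on who is sampled later. A screening PCR exists, and some will fall on day -2 or -1.
- *The primary endpoint is compromised.* The power calculation uses scores 1 to 8 only, and none of these needs a specimen.

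**Conclusion.** The point holds as two separate inconsistencies, both confined to secondary endpoints.

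First, footnote 2 permits visits that cannot yield the specimens required by objectives 1.2.2 and 1.2.3 and by Table 1. On Table 3's assumptions and a telemedicine share common to both arms, half use would leave 72% of control survivors sampled against 58–64% of Neoral survivors; full use, 43% against 15–27%. The actual share is unknown, so neither the size nor the direction of any bias can be stated. PCR is the most exposed, because it is tested at single time points and section 6.5 offers no method for such gaps.

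Second, a PCR in the window that objective 1.2.3 defines is not guaranteed. This affects the stated change from baseline, not the planned between-arm test. Baseline blood markers are scheduled and are not in question.

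**What to change.** 1. Amend footnote 2 so that the day-14 and day-28 contacts of discharged patients are in person or include a local blood draw and swab. Keep telemedicine for assessments that need no specimen. Treat the day-60 PCR mark in the same way or remove it; objective 1.2.3 stops at day 28.
2. Add a PCR mark in the Baseline column and keep the Screening mark, which may be the qualifying test. Alternatively, accept a screening result as the baseline value only if it was taken on day -2 or -1.
3. In section 11.5, commit to reporting the number sampled by arm and discharge status at days 14 and 28, with a sensitivity analysis for PCR results missing after discharge.

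Cost: an amendment to one footnote, one or two schedule marks and a short addition to the analysis text. Some telemedicine contacts become in-person visits or local draws, and some patients have one more swab. No additional patients are needed.
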